Following direct laryngoscopy, the catheter will be introduced orally and inserted through the vocal cords into the trachea to the desired depth of 1-2 cm, the laryngoscope will be carefully removed while the catheter is secured by the fingers of the neonatologist/investigator, who will finally close the neonate's mouth. The correct position of the catheter into the trachea will be confirmed by the visualization of tip depth markings and by the tip-to-lip measurement. The thin catheter presents three different ring markings close to the tip, equal to 1, 2 and 3 cm ([Figure 1C](#)) and helpful to address the depth of insertion beyond the vocal cords. Moreover, the catheter presents markings going from 5 to 9 cm for the tip-to-lip measurement, which represents the standard method to estimate the correct position also of the ETT [\[23\]](#).

After having confirmed the correct position of the catheter into the trachea, the syringe filled with poractant alfa suspension will be connected to the Luer of the catheter and poractant alfa will be instilled over 0.5-3 minutes with careful observation of the neonate's continuous spontaneous breathing. Once the surfactant is administered, the catheter will be removed. Before removing the LISA catheter, it should be fully cleared of surfactant with some additional air. After completion of surfactant administration, ventilatory support may require transient adjustments. Airways suction should not be performed for 1 hour after surfactant instillation, unless signs of significant airway obstruction occur.

If on the first attempt the catheterization of the trachea is not possible within 30 seconds, the laryngoscope should be removed and if required neonate's recovery allowed. Then a second

attempt should be performed for a total number of 3 attempts.

Details of the procedure as well as neonate's vital signs and any occurring adverse event will be recorded according to the time points of the protocol by the team member assisting or observing the procedure.

Figure 1: CHF 6440

Figure 1A
CHF 6440 Full View

Figure 1B
Close-up on CHF 6440 Components

a) Standard Luer

b) Rounded and Soft Tip

[figure not shown]

Figure 1C
Close-up of Markings Present on CHF 6440 Shaft

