6.2.3.4 Conventional Intubation, surfactant administration and brief ventilation

As standard control treatment, neonates spontaneously breathing and stabilized on NIV will receive surfactant via ETT using an approved method of administration, connecting the syringe filled with poractant alfa suspension to:

- a 5-French end-hole catheter inserted into the ETT
or
- the proximal end of the secondary lumen of a dual lumen ETT.

The standard ETT has markings along the side to help identifying the correct distance from the tip of the tube.

Following direct laryngoscopy, the ETT will be inserted through the vocal cords into the trachea to the desired depth. The laryngoscope will be then carefully removed. The correct ETT position into the trachea will be confirmed by the visualization of tip depth markings and by the tip-to-lip measurement. The tube position could be checked by auscultation of the chest to ensure equal aeration of both lungs, observation of chest movement synchronous with positive pressure inflation, enhancement of vital signs, absence of stomach distension while ventilation, and where possible, with the measurement of end tidal CO₂ by colorimetric system on the ETT. Once the tube position is confirmed, the ETT will be secured with adhesive tape or other ways according to the NICU policy.

After administration, manual ventilation can be continued, or the neonate can be connected to the ventilator, or the neonate can be immediately extubated and placed again on NIV. Do not suction airways for 1 hour after surfactant instillation unless signs of significant airway obstruction occur.

If connected to the ventilator, extubation should be performed within one hour after surfactant administration and then the neonate placed again on NIV.

Details of the procedure as well as neonate's vital signs and any occurring adverse event will be recorded according to the time points of the protocol by the team member assisting or observing the procedure.

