9. SAFETY ASSESSMENTS

The following variables will be used to describe the safety of the two procedures:

During procedure for surfactant administration

- Number and percentage of neonates with AEs starting during overall procedure for surfactant administration;
- Number and percentage of neonates with AEs starting during overall procedure for surfactant administration judged related to the procedure;
- Number of AEs occurring during overall procedure for surfactant administration requiring either oxygen alone or an increase in FiO₂ without the need for escalation of invasive or non-invasive ventilator support;
- Number of AEs starting during overall procedure for surfactant administration requiring administration of manual (bag and mask) pressure positive ventilation and related duration of ventilation (non- invasive ventilation);
- Number of AEs starting during overall procedures for surfactant administration requiring endotracheal intubation and related duration of intubation (invasive ventilation);
- Number of AEs starting during overall procedures for surfactant administration requiring circulatory support including administration of crystalloids;
- Number of AEs starting during overall procedures for surfactant administration requiring cardiopulmonary resuscitation including administration of cardiac massage or adrenaline.

After first administration

- Number and percentage of neonates with failed 1st attempt to insert the CHF6440/ETT;
- Number of attempts to the first successful insertion;
- Number of device misallocation (esophageal insertion);
- Number of maneuvers discontinued due to neonate's severe destabilization;
- Duration of the whole procedure (starting from the insertion of laryngoscope up to the removal of the catheter or ETT);
- Duration of surfactant administration (min);
- Heart rate (HR) and respiratory rate (RR) (0, 5, 15 and 30 min, 1 hour, 6 and 12 hours after administration);
- Systolic, diastolic, and mean blood pressure (SBP/DBP/ MBP) (15 and 30 min, 1 hour, 6 and 12 hours after administration);
- Premature Infant Pain Profile (PIPP) score [26] (end of surfactant administration).

During the study

- AEs, including incidence of major neonatal complications of prematurity (listed in [APPENDIX III](#)) and adverse drug reactions (ADRs);
- Blood pressure (SBP, DBP, MBP) at 24, 48, 72, 120 hours post-administration;

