12.2. Populations for analysis

The following populations will be considered for the analysis:

- **Intention-to-Treat population (ITT):** all randomized subjects who will receive at least one dose of study medication.
- **Safety population:** all randomized subjects who will take at least one dose of study medication.

The efficacy analyses population will be performed in the ITT population. The Safety population will be used in the analysis of all safety variables.

In case of deviation between as-randomized treatment and treatment actually received, the treatment actually received will be used in the safety analyses (i.e. an as-treated analysis will be performed).

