12.3.1. Descriptive Statistics

General descriptive statistics for numeric variables will include the n (number of observed values), the mean, the standard deviation, 95% CI, the median, the minimum, and the maximum values. For categorical variables, the number and percent of subjects with a specific level of the variable will be presented.

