12.3.5. Safety variables

Adverse Events and Neonatal Morbidities

- Number and percent of neonates reporting AEs started during procedure for surfactant administration as well as AEs started during the procedure and judged related to the procedure will be summarized by treatment group.

For LISA group, any AE assessed as related to CHF 6440 catheter will be considered procedure-related.

These events will be also summarized by treatment group based on action required, if any (i.e. supplementary oxygen or transient increase in FiO₂, manual positive pressure ventilation, endotracheal intubation, administration of, crystalloids, or cardiopulmonary resuscitation or administration of adrenaline). The duration of endotracheal intubation and positive pressure ventilation will be

summarized as well.

A subgroup analysis of AEs during procedure for surfactant administration will be performed based on the use of sedation and/or analgesia (Yes/No).

- Incidence of AEs including neonatal complications of prematurity (see [APPENDIX III](#) for complete list), related AEs (ADRs), serious AEs (SAEs) and AEs leading to death will be summarized by treatment group both in term of frequency of neonates with at least one AE and in term of frequency of AEs (number of events). All the aforementioned categories of AEs will be summarized by System organ Class (SOC) and Preferred Term (PT).
- Frequency of neonates with major neonatal morbidities at discharge or 40 weeks PMA (whichever comes first) will be summarized by treatment group.

Vital Sign

- Vital signs parameters (SBP, DBP MBP, HR and RR) will be summarized as absolute and the change from baseline (pre-procedure) by treatment group using descriptive statistics.

Pain assessment

- PIPP score will be summarized by treatment group by means of descriptive statistics.

First administration

- Number of 1st failed attempt to insert the catheter/ETT will be summarized by treatment group. Percentage of neonates with 1st failed attempt will be compared between group using the Cochran-Mantel-Haenszel adjusted for gestational age group. The CMH adjusted difference with its 95% CI will be presented.
- Number of attempts to the first successful insertion will be summarized by treatment group by means of descriptive statistics.
- Number of device misallocation (i.e., esophageal intubation) will be summarized by treatment group by means of descriptive statistics.

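### Attempts to first successful insertion has no defined value when the assigned device is never placed, and the dosed-only and as-treated rules can remove complete LISA failures from the LISA insertion results

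*Protocol*

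**What the plan says.** Section 9 of the protocol lists "Number of attempts to the first successful insertion" among the variables after first administration. Section 12.3.5 gives its analysis: "Number of attempts to the first successful insertion will be summarized by treatment group by means of descriptive statistics". For numeric variables, Section 12.3.1 asks for the number of observed values plus "the mean, the standard deviation, 95% CI, the median, the minimum, and the maximum values".

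The two arms are described differently. If the first LISA attempt fails, Section 6.2.3.3 says that a second "attempt should be performed for a total number of 3 attempts". It does not say what follows a third failure. For the control arm, Section 6.2.3.4 says "Following direct laryngoscopy, the ETT will be inserted through the vocal cords into the trachea to the desired depth" and gives no number of attempts.

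A companion variable is formally compared in Section 12.3.5: "Percentage of neonates with 1st failed attempt will be compared between group using the Cochran-Mantel-Haenszel adjusted for gestational age group", with an adjusted difference and 95% CI.

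Section 12.2 defines the Safety population as "all randomized subjects who will take at least one dose of study medication". Where the treatment given differs from the one assigned, "the treatment actually received will be used in the safety analyses (i.e. an as-treated analysis will be performed". The population labelled ITT also requires a dose. Section 12.3.2 leaves the handling of missing data to the SAP.

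**The concern.** A count of attempts up to success exists only if success occurs. A LISA neonate in whom three attempts fail has no such count, while an ETT neonate placed on a later attempt contributes that later number. A summary over neonates with a value would then rest on early successes in one arm and on all eventual successes in the other.

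No other listed variable fills the gap. First-attempt failure does not separate later success from complete failure. The count of discontinued maneuvers covers severe destabilization only. Nothing counts neonates whose assigned device was never placed, or who were converted to the other device.

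Section 12.2 widens the problem beyond one descriptive line. If complete LISA failures leave the LISA group, because they were not dosed or because they were dosed through an ETT, they leave every first-administration variable for that group. Whether CHF 6440 could be placed is a basic result for a trial whose main objective is the safety of giving surfactant through it, and the worst placement outcome is the one most exposed to loss.

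**Working it through.** **Plan's own figures.** The protocol gives no expected attempt count, success rate or effect size, so there is nothing to reproduce beyond the allocation: 150 × 2/3 = 100 LISA and 150 × 1/3 = 50 ETT (Section 12.1).

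**Inputs.** LISA limit of 3 (Section 6.2.3.3). ETT limit: none stated (Section 6.2.3.4), modelled as no limit. Per-attempt success p: not in the document, assumed 0.5 to 0.9, equal in both arms, attempts independent; q = 1 − p.

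**Formulas.**
- Share of LISA neonates with no value: q³.
- Probability of at least one such neonate among 100: 1 − (1 − q³)^100.
- LISA mean among those placed within 3: p(1 + 2q + 3q²) / (1 − q³).
- ETT mean without a limit: 1/p.
- Approximate SE of the difference in means, using the unlimited SD in both arms: (√q / p) × √(1/100 + 1/50).
- LISA first-attempt failure: q if complete failures stay in the arm; (q − q³) / (1 − q³) if all of them leave it.

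Worked case, p = 0.6: q³ = 0.064. LISA mean = 0.6 × (1 + 0.8 + 0.48) / 0.936 = 1.368 / 0.936 = 1.46. ETT mean = 1 / 0.6 = 1.67. First-attempt failure falls from 0.400 to (0.400 − 0.064) / 0.936 = 0.359.

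| Assumed p | LISA with no value, per 100 | P(at least one) | LISA mean | ETT mean | Difference | Approx. SE | LISA first-attempt failure: kept / removed |
|---|---|---|---|---|---|---|---|
| 0.5 | 12.5 | 1.00 | 1.57 | 2.00 | 0.43 | 0.24 | 50% / 42.9% |
| 0.6 | 6.4 | 0.999 | 1.46 | 1.67 | 0.21 | 0.18 | 40% / 35.9% |
| 0.7 | 2.7 | 0.94 | 1.35 | 1.43 | 0.08 | 0.14 | 30% / 28.1% |
| 0.8 | 0.8 | 0.55 | 1.23 | 1.25 | 0.02 | 0.10 | 20% / 19.4% |
| 0.9 | 0.1 | 0.10 | 1.11 | 1.11 | 0.003 | 0.06 | 10% / 9.9% |

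The median is 1 in both arms throughout (at p = 0.5, taking the lower median). Of the values tried, the difference in means exceeds one SE only at 0.6 and below.

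**Effect of keeping the failures.** If LISA failures are kept and scored 4 (more than 3), the LISA mean becomes p(1 + 2q + 3q²) + 4q³ = 1.875, 1.624, 1.417, 1.248 and 1.111 for p = 0.5 to 0.9. The ETT means are 2.000, 1.667, 1.429, 1.250 and 1.111. Most of the artificial gap closes.

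**The case against.** A reader might infer that the protocol drops complete LISA failures and so makes LISA look easier to perform. The text does not go that far. It is silent on how such a neonate is recorded, and missing-data rules are left to the SAP, which is not at hand. Several further points stand:

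- The attempts variable is descriptive and untested, and no decision rests on it.
- The number of observed values must be shown, so a shortfall against the arm total would be visible.
- First-attempt failure does not depend on eventual success. A complete failure who stays in the LISA group counts there, and under equal success the two arms would then agree.
- The figures depend on assumed success rates and on ETT attempts continuing without limit. The protocol does not say that fourth or fifth ETT attempts will occur, and if operators stop near three the asymmetry in the means largely goes. Nor is the LISA figure strictly bounded at 3, since that limit is worded as a recommendation.

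Two things are not answered. First, these values are not lost data: they do not exist under the definition that the protocol fixes, and no other variable counts them. Second, the defence that first-attempt failure is safe holds only while the neonate remains in the LISA group, and Section 12.2 does not guarantee that.

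**Conclusion.** The point holds as a gap in definition combined with a population rule, not as a demonstrated bias. The variable has no defined value for a neonate whose assigned device is never placed, the attempt rules are stated for one arm only, and Section 12.2 can take complete LISA failures out of the LISA first-administration results. Conversion to the ETT arm is a possible consequence of the as-treated rule, not a stated one.

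Under equal assumed success the difference in means runs from 0.43 attempts at 0.5 to 0.003 at 0.9, and is below one SE at 0.7 and above. If all complete failures leave the arm, LISA first-attempt failure is understated by 7.1 percentage points at 0.5 (50 − 42.9), 4.1 at 0.6 (40 − 35.9), and 1.9 or less from 0.7 upward (30 − 28.1). The documents do not support saying that LISA will look easier overall. The change is still worth making because it is cheap and reports an outcome that the plan otherwise has no line for.

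**What to change.** In Sections 9 and 12.3.5, replace the numeric summary, in both arms, by a table of attempts: placed on attempt 1, on attempt 2, on attempt 3, or not placed within 3. ETT placements on attempt 4 or later go in the last category. The denominator is all randomized neonates in whom a laryngoscope was inserted, by assigned arm. Add two lines per arm: n (%) with the assigned device never placed, and n (%) converted to the other device.

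In Section 12.2, state that the insertion variables, including first-attempt failure, are an exception to the dosed-only and as-treated rules. Without this, the new table would contradict the population definitions.

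Sections 6.2.3.3 and 6.2.3.4 should be reconciled on how an attempt is counted in each arm. This proposes no clinical limit: the third-attempt cut is a reporting category taken from the existing LISA text.

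The cost is wording in three sections and one extra table, drawing on the same insertion record. LISA delivery results may look slightly less favourable.

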3. STUDY DESIGN

This is an open-label, multicenter, randomized and controlled study. Approximately 25 investigational sites will be involved in US. Neonates will be evaluated according to the selection criteria and then randomized to surfactant treatment via LISA or standard administration procedure ([Table 1](#)). The enrollment will be staggered: the gestational age will be restricted to 27⁺⁰ weeks up to 28⁺⁶ completed weeks until safety evaluation by ISMB is performed for the first 15 neonates. Provided no safety concerns are raised, the enrollment will then be extended to the whole population (i.e. 25⁺⁰ weeks up to 28⁺⁶ completed weeks).

[figure not shown]
Enrolled neonates will be evaluated:

- until discharge,
- until 40 weeks PMA (if still in hospital),
- if discharge occurs before 36 weeks, the last evaluation will be at 36 weeks PMA.

This period represents the main phase of the trial.

Their final assessment of development will be at 24-month corrected age as a separate stand-alone visit. This 24-month clinical assessment will be analyzed and evaluated separately from the initial part of the study and will be object of an addendum to the initial core clinical study report.

Table 1: TIMETABLE

End of the trial

The end of the trial will correspond to the last evaluation of the last neonate from the recruiting site or from the continuing care site in case the treated baby was transferred from the original recruiting site. The last evaluation could be:

- the date of the assessment for BPD diagnosis (i.e. 36 weeks PMA) if the patient is discharged home before 36 weeks PMA,
- discharge home (if discharged between 36 weeks and 40 weeks PMA), or
- 40 weeks PMA (if still in hospital).

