7.1.1 Pre-randomization Period - On admission prior to study treatment administration

The study will be explained to the parents of a potentially eligible neonate prior to birth, if possible, giving the parents the maximum time to make an informed choice. Once parental/maternal written informed consent has been obtained either prior to or after birth, the neonate's eligibility to take part in the study will be assessed according to the post-birth inclusion and exclusion criteria. If the neonate becomes eligible, then the medical history of the mother, the complications during pregnancy and the prenatal use of corticosteroids will be collected.

If the neonate becomes eligible, then the following information will be collected:

- Birth weight, occipital-frontal circumference (OFC), length;
- Apgar score at 1 and 5 min from birth;
- All medical conditions diagnosed before treatment drug administration, to be reported as "Medical History". To this group should be added thereafter those congenital conditions that, even if already present at birth, could be diagnosed after study treatment administration (including: major organ malformations, genetic diseases and/or chromosomal abnormalities);
- Concomitant medications;
- Clinical signs of RDS, such as tachypnea, retractions, nasal flaring, expiratory grunt;
- SpO₂ along with vital signs (systolic, diastolic and mean blood pressure, heart rate, respiratory rate);

- Fraction of inspired oxygen (FiO_2);
- Type of respiratory support (CPAP, BiPAP, NIPPV);
- Blood gas analysis (values of pH, pCO_2 , pO_2 , HCO_3 , BE, lactate), when feasible.

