- Evaluation of respiratory support: any change in non-invasive ventilation, need for intubation and invasive mechanical ventilation with the relevant dates and times;
- Evaluation of oxygen alone use: duration of needing supplementary oxygen with the relevant dates and times;
- Further neonatal concomitant medications and adverse events (including worsening of conditions pre-existing to treatment) as well as changes in those already reported; major complications of prematurity (listed in [APPENDIX III](#)) to be recorded among adverse events.

7.1.6 28 days PNA

The following information will be collected:

- FiO₂ (highest recorded value), SpO₂, HR and RR at the same time;
- Evaluation of respiratory support: any change in non-invasive ventilation, need for intubation and invasive mechanical ventilation with the relevant dates and times;
- Evaluation of oxygen alone use: duration of needing supplementary oxygen with the relevant dates and times;
- Further neonatal concomitant medications and adverse events (including worsening of conditions pre-existing to treatment) as well as changes in those already reported; major complications of prematurity (listed in [APPENDIX III](#)) to be recorded among adverse events.

In case the neonate was discharged home (either by the recruiting site or by a continuing care site) prior to 28 days of life, the neonate should be recalled for an on-site clinic visit at the recruiting site. If not feasible, any effort should be made to collect information about the occurrence of any adverse events as well as about any change in concomitant medications. The Investigator should contact the family pediatrician to collect the relevant information.

In case the treated neonate was transferred to a continuing care site prior to 28 days PNA and the neonate is still hospitalized there, the neonate should be recalled at the recruiting site for the visit. If this is not feasible, the visit can be replaced by a contact/phone call by the Investigator to the physician of the continuing care site to collect relevant information and check the occurrence of any other adverse event as well as of any change in concomitant medications.

7.1.7 36 weeks PMA

The following information will be collected:

- Weight
- FiO₂ (highest recorded value) SpO₂, HR and RR at the same time;

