7.1.8 Discharge home or 40 weeks PMA (whichever comes first)

The below assessments will be performed at discharge, or at 40 weeks PMA if the infant is still in hospital. The following information will be collected:

- SpO₂, HR and RR at the same time;
- Weight, OFC and length;
- Evaluation of respiratory support (if present): non-invasive respiratory support, or invasive mechanical ventilation and related FiO₂;
- If receiving respiratory support via nasal cannulae: evaluation if flow rate ≤ 2 l/min or > 2 l/min
- Evaluation of feeding status, hearing screen status, medications for respiratory problems;

- Assessment of relevant neonatal co-morbidities, their severity and treatment;
- Further neonatal concomitant medications and adverse events (including worsening of conditions pre-existing to treatment) as well as changes in those already reported.

In case the infant had been transferred to a continuing care site, the recruiting site is responsible for the proper continuation of data collection and documentation of the primary and secondary outcomes. The investigator of the recruiting site should keep contacts and provide the continuing care site with written instruction about management of the above as well as for the reporting of serious AE, if any. The recruiting site should receive a discharge letter clarifying as much detailed information as possible the progress in subject's conditions.

Routine clinical safety data included in the discharge home summary letter should be sought to complete data collection.

If the discharge home coincides with the 36 weeks PMA visit, both assessments should be completed and recorded in the eCRF.

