- Heart Rate (HR) and respiratory rate (RR), at 24, 48, 72, 120 hours post-administration and 28 PNA, 36 weeks PMA, discharge home or 40 weeks PMA whichever comes first;
- Incidence of BPD at 36 weeks PMA;
- Death/BPD incidence at 36 weeks PMA, defined as the incidence of the neonates who are dead or alive but with a diagnosis of BPD at the time of assessment (i.e. 36 weeks PMA);
- Mortality at Day 28 PNA and 36 weeks PMA;
- Oxygen use (alone and/or during invasive and non-invasive ventilation) at Day 28 PNA and 36 weeks PMA;
- Weight, OFC and length at discharge home or 40 weeks PMA;
- Feeding and hearing status at discharge home or 40 weeks PMA, whichever comes first;
- Incidence of major neonatal morbidities at discharge home or 40 weeks PMA, whichever comes first;
- Neonates needing invasive ventilation or non-invasive respiratory support at discharge home or 40 weeks PMA;
- Neonates needing respiratory medications at discharge home or 40 weeks PMA.

24 months (± 3 months) corrected age

(This stand-alone assessment will be analyzed and reported separately from the main phase)

- Health status questionnaire, including:
 - ✓ Bayley Scales of Infant Development (cognitive and language scores);
 - ✓ Feeding method: spoon, nasogastric tube or gastrostomy;
 - ✓ Cerebral palsy evaluation;
 - ✓ Seizure evaluation;
 - ✓ Vision, hearing and communication evaluation;
 - ✓ Clinical assessment of respiratory conditions and morbidity;
 - ✓ Vital signs (SBP/DBP/MBP, HR, RR);
 - ✓ Growth assessment (Weight, OFC and length).

10. ADVERSE EVENTS REPORTING**10.1. Definitions**

An **Adverse Event** is “any untoward medical occurrence in a subject or clinical trial subject administered a medicinal product and which does not necessarily have a causal relationship with this treatment”.

An adverse event can therefore be any unfavorable and unintended sign (including abnormal laboratory finding), symptom, or disease temporally associated with the use of an investigational product, whether or not considered related to the investigational product.

An **Adverse Drug Reaction** is an “untoward and unintended responses to an investigational medicinal product related to any dose administered”.

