- Number of maneuvers discontinued due to neonate's severe destabilization will be summarized by treatment group by means of descriptive statistics.
- Duration of surfactant administration (min) and overall procedure for surfactant administration will be compared between treatment groups by using the Mann-Whitney U- test.

Mortality and BPD

- Death/BPD incidence at 36 weeks PMA will be compared by treatment by means of CMH test, adjusting for GA group and related 95% confidence interval will be provided.

- The incidence of BPD at 36 weeks PMA will be compared by treatment as for Death/BPD incidence.
- The mortality at 36 weeks PMA and at Day 28 will be compared by treatment as for Death/BPD incidence.
- Oxygen use at Day 28 (alone and / or during any kind of MV) will be compared by treatment as for Death/BPD incidence.

Other safety variables

- Feeding and hearing status at discharge or 40 weeks PMA (whichever comes first) will be summarized by treatment group by frequency distributions.
- Weight, OFC and length at discharge home or 40 weeks PMA will be summarized by treatment group by descriptive statistics.
- Neonates needing invasive or non-invasive respiratory support at discharge home or 40 weeks PMA will be summarized by treatment group by frequency distribution
- Neonates needing respiratory medications at discharge home or 40 weeks PMA will be summarized by treatment group by frequency distribution

Health status questionnaire at 24 months (± 3 months) corrected age

(This stand-alone assessment will be analyzed and reported separately from the main phase)

- Bayley Scales of Infant Development (cognitive and language scores) will be summarized using descriptive statistics by treatment group and BSID version (III or IV).
- Vital signs and all other variables collected through the questionnaire (i.e., anthropometric measures, cerebral palsy, seizures, feeding method, functional disability and respiratory morbidity) will be summarized by treatment group by frequency distribution or descriptive statistics, as appropriate.

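### Weight, head circumference and length are summarised by arm at discharge or 40 weeks PMA with no allowance for age, so a difference in discharge timing would appear as a difference in size

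*Protocol*

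**What the plan says.** Protocol Section 9 lists "Weight, OFC and length at discharge home or 40 weeks PMA" among the safety variables. Section 12.3.5, under other safety variables, and the outline at the front both give the same analysis: "Weight, OFC and length at discharge home or 40 weeks PMA will be summarized by treatment group by descriptive statistics". Section 12.3.1 defines descriptive statistics for a numeric variable as the number of observations with "the mean, the standard deviation, 95% CI, the median, the minimum, and the maximum values".

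Section 7.1.8 sets the time of measurement: "The below assessments will be performed at discharge, or at 40 weeks PMA if the infant is still in hospital". Section 3 shows that discharge can come earlier than the 36-week visit: "if discharge occurs before 36 weeks, the last evaluation will be at 36 weeks PMA". The age at which growth is recorded can therefore lie anywhere from below 36 weeks up to 40 weeks PMA.

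Two other growth records exist in the main phase. At baseline, Section 7.1.1 collects "Birth weight, occipital-frontal circumference (OFC), length". At 36 weeks PMA, Section 7.1.7 collects weight ("The following information will be collected: - Weight") but not head circumference or length, and Section 12.3.5 lists no summary of that weight.

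**The concern.** Infants near term grow quickly, so size depends strongly on the day of measurement. Here that day is largely set by discharge, which is an outcome. Treatment could affect it: Section 1.2 reports less ventilation and less BPD with less invasive surfactant methods, and the trial is open-label. If one arm goes home sooner, its infants are measured younger and look smaller, although they may be growing equally well. Faster recovery would then read as poorer growth. If that arm stays longer, the distortion runs the other way.

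The planned tables would not reveal the cause. Sections 12.3.4 and 12.3.5 list no summary of age at discharge or length of stay. For the 24-month visit, by contrast, Section 12.3.3 does summarise age and corrected age.

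**Working it through.** The protocol gives no power calculation, standard deviation, growth rate or discharge age for these variables, so there is no figure of its own to reproduce. The only relevant number is the sample size in Section 12.1: 150 infants at 2:1, that is 100 and 50.

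**Assumptions (none from the documents).** Weight gain 25 to 35 g/day. Difference between arms in mean age at measurement 3 to 7 days. Standard deviation of weight 450 g. Infants measured: 95 and 47. Growth identical in both arms.

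**Apparent gap in mean weight** = daily gain × difference in mean age at measurement.
- Low end: 25 × 3 = 75 g.
- High end: 35 × 7 = 245 g.
- No difference in age: 0 g.

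**Head circumference and length**, at an assumed 0.5 to 1.1 cm/week:
- 3 days: 0.5 × 3/7 = 0.2 cm to 1.1 × 3/7 = 0.5 cm.
- 7 days: 0.5 to 1.1 cm.

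**Scale against sampling error.** The standard error of a difference in means would be 450 × √(1/95 + 1/47) = 80 g, so the gap is 75/80 = 0.9 to 245/80 = 3.1 standard errors. This is only a yardstick, because the protocol plans no difference between arms.

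**What the reader would see.** Section 12.3.1 gives a 95% CI, which for these variables means one for each arm. The half-widths would be about 1.96 × 450/√95 = 90 g and 1.96 × 450/√47 = 129 g, together 219 g. A gap of 75 g would be lost in the overlap. A gap of 245 g would leave the two intervals apart.

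**Simulation check.** This used 3,000 runs with 100 against 50 infants, one growth line for both arms (30 g/day), residual standard deviation 300 g, and age at measurement with standard deviation 2 weeks, limited to 34 to 40 weeks.

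| Difference in mean PMA at measurement (weeks) | Unadjusted weight difference (g) | Difference after adjusting for PMA (g) |
|---|---|---|
| 0.00 | 1 | 1.5 |
| −0.41 | −86 | 0.4 |
| −0.84 | −177 | −0.1 |
| −1.29 | −270 | −0.4 |

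The unadjusted difference is the age difference times 210 g/week (for example 0.41 × 210 = 86 g). It vanishes once age at measurement is taken into account. The 40-week cap narrows the spread of ages but does not remove the effect.

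**The case against.** **No comparison is planned.** Section 12.3.5 says that death/BPD, mortality, oxygen use and procedure durations will be compared, but says only that growth will be summarised. A reader might infer that a growth test will be biased or that a false finding will be declared. The documents do not support that: there is no test, adjusted difference or between-arm interval for growth. This stands, and it limits the harm to a misleading descriptive table.

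**Standardisation belongs in the SAP.** Section 12.3 defers detail to a separate document that is not at hand, and the protocol does not rule out z-scores. This stands in part. But the protocol itself fixes the variable time point and names the summary. Where it wants a derived quantity it says so: change from baseline for vital signs, change from pre-treatment for blood gases, Bayley scores by version. For growth it names none.

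**Size at leaving the unit is worth describing.** It sits beside feeding, hearing and respiratory support at the same visit. Growth is not named in the primary objective (Section 2.1), and it is measured again at 24 months corrected age, which does not depend on discharge. This is fair, and it is why the measured values should stay in the table.

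**The size is wholly assumed.** This stands. A reader might infer that LISA infants will look smaller. The documents give no discharge ages for either arm, so neither the direction nor the amount can be predicted.

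**The 36-week weight is no clean substitute.** It is tempting to make it the main growth result because its age is nominally fixed. Under Sections 7.1.7 and 7.2.3, however, infants discharged before then without oxygen or respiratory support need not attend on site, so weights may be missing mainly for those who left earliest. Table 3 also allows 4 days either side, and head circumference and length are not taken. This objection stands in full.

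**Conclusion.** The point holds as a conditional weakness in a descriptive safety summary. The protocol records three growth measures at an age that arises after randomisation and may depend on treatment, then summarises them by arm with nothing that separates growth from timing. If mean PMA at measurement differs by 3 to 7 days, the table would show a weight gap of 75 to 245 g under identical growth, given an assumed 25 to 35 g/day. If discharge ages are equal, there is no bias.

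The mechanism is certain, but whether it will occur, in which direction and how strongly is not known from the documents. No efficacy result and no formal test is affected. The point still merits a change because the better summary uses data already collected and costs little.

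**What to change.** In Section 12.3.5, and in the matching outline entry:

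- Summarise by arm the sex- and PMA-specific z-scores of weight, head circumference and length at the measurement date, and their change from the z-scores at birth. Name the growth reference in advance.
- Show PMA at measurement by arm in the same table. A z-score removes the age effect only as far as the reference follows these infants' growth, so the reader needs the ages as well.
- Keep the measured grams and centimetres as description of the infant at that visit.
- If wanted, add weight at 36 weeks PMA as a supportive summary, with the number missing by arm. Do not make it the main growth result.

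The inputs are already in the plan: birth measures (Section 7.1.1), sex and gestational age (Section 12.3.3) and visit dates (Appendix II). No visit, measurement or aspect of care changes. The cost is one derivation against a reference growth chart and a few more rows in one table.
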